## 21.6 Assessment of SAEs by the PI (or delegate)

The PI (or delegated individual) is responsible for assessing all reported SAEs for seriousness, causality and expectedness.

## 21.6.1 Relatedness/causality

The assessment of "relatedness" to the trial intervention is the responsibility of the PI at site or an agreed designee according to the following definitions:

Table 7: Relatedness and causality

Relationship to intervention	Attribution (Causality)	Description	
Unrelated	Unrelated	The AE is clearly NOT related to the intervention	
	Unlikely	The AE is doubtfully related to the intervention	
Related	Possible	The AE may be related to the intervention	
	Probable	The AE is likely related to the intervention	
	Definite	The AE is clearly related to the intervention	

For the purpose of safety reporting interventions are defined as self-directed rehabilitation or physiotherapist-supervised rehabilitation.

## 21.7 Review of SAEs by the Sponsor/Clinical Trials Unit (CTU) Nominated Person

An appropriately qualified person will review the SAE and raise any queries with the reporting site. If the site has not provided an assessment of causality and has not responded to the query, it will be assumed that the event reported is related to the trial procedures/intervention. The site will be encouraged to respond and if a response is not provided, the CI will be consulted by the central trial team and the central trial team will complete the Sponsor part of the SAE report.

## 21.8 Reporting of SAEs to the Research Ethics Committee (REC)

All SAEs that are assessed as related and unexpected will be submitted to the REC within 15 days of the CTU/Sponsor becoming aware of the event.

#### 21.9 Unblinding of SAEs for reporting to the REC

Not applicable as the trial team are already unblinded.

## 21.10 Follow-up of SAEs

If the SAE is an unexpected, related event then follow up information must be provided as requested by the central trial team. A follow-up report must be completed when the SAE resolves, is unlikely to change, or when additional information becomes available.

#### 22 PREGNANCY

If a participant does become pregnant during their participation in the trial, it does not need to be reported due to the nature of the intervention as concluded in the risk assessment of the trial.

#### 23 STATISTICAL CONSIDERATIONS

## 23.1 Statistical Analysis Plan (SAP)

The statistical aspects of the trial are summarised here with details fully described in a SAP that will be drafted early in the trial and finalised prior to the final analysis data lock, or any planned interim comparative analyses. The SAP will be written by the Trial Statistician in accordance with the current OCTRU SOPs. Any changes or deviations from the original SAP will be described and justified in any protocol amendments, final report and/or publications, as appropriate.

## 23.2 Sample Size/Power calculations

The primary outcome measure is the OSS at 6 months post-randomisation. Previous studies have demonstrated a minimum clinically important difference (MCID) of 5 points and a standard deviation of 12 (1). One method for choosing the non-inferiority margin is to take half the MCID and this is the method used in this trial. In real terms, a 2.5 point worse score equates to dropping one level on more than two of the twelve questions e.g. moving from little to moderate difficulty in more than two functional tasks such as household shopping and hanging clothes in a wardrobe. To ensure the acceptability of this margin with patients and clinicians we undertook consultations with stakeholder representatives. A 5% worse outcome overall (2.5/48) would be acceptable to avoid the burden of multiple outpatient visits and is sufficient to change clinical decision making. Primary outcome data provided by 970 participants at 6 months will provide 90% power at 2.5% (1-sided) significance to detect whether self-directed rehabilitation is non-inferior to standard physiotherapist-supervised rehabilitation based on a non-inferiority margin of 2.5. Allowing 20% loss to follow-up yields an overall sample size of 1214 (607 per group).

#### 23.3 Description of Statistical Methods

Standard descriptive statistics will be used to summarise the baseline participant demographic characteristics by treatment group using means with standard deviation or medians with interquartile ranges as appropriate for continuous variables and numbers with percentages for binary or categorical variables. It is anticipated that all statistical analyses will be undertaken using Stata (StataCorp LP, www.stata.com) or other well-validated statistical software.

A non-inferiority trial aims to demonstrate that a new treatment is not clinically worse than the active control by more than a predefined amount and therefore the interest is one-sided. The new treatment may be better than the control, but it must not be inferior. We therefore define a maximum difference between the two groups in a given direction we are prepared to tolerate and

still consider the new treatment clinically not inferior to the standard treatment. This difference is the non-inferiority margin ( $\Delta_M$ ). We then test the null hypothesis that a difference greater than  $\Delta_M$  exists in favour of the control ( $H_0$ :  $\Delta \geq \Delta_M$ ). This is assessed by constructing a 95% confidence interval for the difference between the two treatments ( $\Delta$ ) which should be above the non-inferiority margin for the new treatment to be declared non-inferior and reject the null hypothesis in favour of the alternative ( $H_A$ :  $\Delta > -\Delta_M$ ). To estimate  $\Delta$ , the primary outcome measure, OSS at 6 months will be compared between treatment groups as the dependent variable in a mixed effects linear regression model adjusting for the minimisation factors (age and centre). A fixed effect will be used to account for age and a random effect will be included to account for any heterogeneity due to recruitment centre.

The primary analysis will be performed using a treatment policy, in which all randomised participants with available data are analysed according to their treatment allocation regardless of whether intercurrent events occur (30, 31). Given the nature of the interventions as described in Section 13, any trial-specific intercurrent events which are likely to occur in the trial setting and not in routine clinical practice are expected to be non-significant. For example, it is possible for participants in both self-directed rehabilitation and usual care groups to access further physiotherapy treatment. To assess the impact of such intercurrent events or similar on the non-inferiority conclusion, we will consider defining additional secondary estimands. Details of the estimands and estimator strategy will be defined in the SAP and finalised following a blinded review of the data before the primary outcome analysis data lock (32).

Additional analyses including data from all timepoints in a multilevel linear regression model will be used to explore the recovery trajectory between the two groups for the OSS score using the area under the curve (AUC) based on a summary statistics approach (33). Similar mixed effects linear regression models will be used to analyse continuous secondary outcomes (PROMIS, EQ5D- 5L, SEE Scale) over time. The number and proportion of participants experiencing complications will be summarised by treatment group and compared using an adjusted logistic regression model if sufficient complications occur.

Results will be reported in line with the CONSORT statement and any appropriate extensions and will be described fully in a separate SAP. A single final unblinded statistical analysis will take place after all follow-up has been completed, and sufficient time has been allowed for data collection and cleaning.

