#### 15 RANDOMISATION

## 15.1 Timing of randomisation

Randomisation will only be performed when informed consent has been obtained, eligibility confirmed, and baseline questionnaires completed.

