#### 17.1 Overview

Table 4 shows scheduled assessments for the trial.

After consent, baseline demographic data as well as patient-reported outcome measures will be collected prior to randomisation. Data collection will be completed by the participant, a member of the research team will be available to assist if required.

After randomisation, patient-reported outcomes, resource use and health-related quality of life, Complications and shoulder exercise data will be collected from participants via electronic or postal questionnaires at 2, 4 and 6 months. Additional data collection on physiotherapy session attendance will be collected from those participants allocated to the usual care group. Recruitment centres will be asked to review the participants' medical records and report complications up to 6 months post-randomisation. Data collection will be centrally managed by the central trial team at the University of Oxford.

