## 23.8 Level of Statistical Significance

Non-inferiority comparisons will use one-sided 2.5% significance which is equivalent to the lower bound of the 95% confidence interval being compared to the non-inferiority margin. If the Self-directed rehabilitation is found to be non-inferior to physiotherapist-supervised rehabilitation then superiority will also be tested at 2.5% (1-sided) significance. The remaining superiority comparisons and secondary outcome analyses will use a two-sided 5% significance and 95% confidence intervals throughout.

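### The primary model names age and centre but not baseline OSS, which every participant completes before randomisation: a missed gain in precision, and a covariate list that differs between sections 23.3 and 23.9

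*Protocol*

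**What the plan says.** Section 23.3 gives the primary analysis of 6-month OSS as a "mixed effects linear regression model adjusting for the minimisation factors (age and centre"), with age as a fixed effect and centre as a random effect. It carries similar models over to PROMIS, EQ-5D-5L and SEE. No analysis section names baseline OSS.

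The baseline scores exist. Section 17.1 says that "baseline demographic data as well as patient-reported outcome measures will be collected prior to randomisation". Table 4 and section 17.3.1 list two baseline OSS values, a recalled pre-injury score and a post-injury score. Section 15.1 makes completion a condition of entry: "Randomisation will only be performed when informed consent has been obtained, eligibility confirmed, and baseline questionnaires completed".

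The decision rule is in section 23.8: "Non-inferiority comparisons will use one-sided 2.5% significance which is equivalent to the lower bound of the 95% confidence interval being compared to the non-inferiority margin".

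Section 23.9, on missing data, describes a multilevel model adjusted for the minimisation factors or for prognostic factors, and does not say which these are. Section 23.1 leaves full detail to the SAP.

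**The concern.** Non-inferiority here depends on whether the lower confidence limit clears the margin, so the width of the interval bears directly on the result. The baseline value of the same scale is a natural prognostic covariate for a patient-reported outcome, and here it should be available for almost everyone. A model with age and centre alone uses none of that information.

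The second issue is prespecification. Section 23.3 lists two covariates, while section 23.9 leaves room for others without naming them. The trial is open-label. Table 5 gives the statisticians access to allocation for the closed monitoring reports, and section 23.1 lets the SAP be finalised as late as just before the final data lock. The covariates of the primary model are better fixed in one place and early.

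**Working it through.** **Inputs from the protocol.** Section 23.2 gives a "minimum clinically important difference (MCID) of 5 points and a standard deviation of 12", a calculation "based on a non-inferiority margin of 2.5", and this target: "Primary outcome data provided by 970 participants at 6 months will provide 90% power at 2.5% (1-sided) significance". Allocation is 1:1 (section 15.3) and allowed loss is 20% (section 23.2).

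**Assumptions.** The true difference is 0. This is not stated, but it is the value that reproduces the plan's figure. The correlation *r* between baseline and 6-month OSS is not given, so I use a range of 0.1 to 0.5, read as the partial correlation given age and centre.

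**Step 1: reproduce the plan.**
n per group = 2 × 12² × (1.960 + 1.282)² / 2.5² = 484.2, rounded up to 485, so 970 in total. Allowing for loss: 485 / 0.8 = 606.25, rounded up to 607 per group, so 1214. Both of the plan's figures reproduce, and neither takes credit for any covariate.

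**Step 2: precision without baseline OSS.**
SE = 12 × √(2/485) = 0.7706. Half-width = 1.96 × 0.7706 = 1.51. Power = Φ(2.5/0.7706 − 1.96) = 90.0%.

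**Step 3: precision with baseline OSS.**
Adjusted SE = 0.7706 × √(1 − r²). Power = Φ((2.5 + d)/SE − 1.96), where d is the true difference (negative if self-directed care is worse). The worst observed difference that still passes is −2.5 + half-width. The unadjusted number giving the same precision is 970/(1 − r²).

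| Assumed partial r | 95% half-width | Interval narrower by | Power, d = 0 | Power, d = −0.5 | Worst passing difference | Equivalent N |
|---|---|---|---|---|---|---|
| 0 | 1.51 | – | 90.0% | 73.7% | −0.99 | 970 |
| 0.1 | 1.50 | 0.5% | 90.3% | 74.2% | −1.00 | 980 |
| 0.2 | 1.48 | 2.0% | 91.2% | 75.5% | −1.02 | 1,010 |
| 0.3 | 1.44 | 4.6% | 92.5% | 77.7% | −1.06 | 1,066 |
| 0.4 | 1.38 | 8.3% | 94.3% | 80.8% | −1.12 | 1,155 |
| 0.5 | 1.31 | 13.4% | 96.3% | 85.0% | −1.19 | 1,293 |

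The table takes 12 as the SD that remains after age and centre. If those terms already explain part of the variance, the top row starts from a narrower interval. The proportional narrowing in the third column is unchanged, provided *r* is the partial correlation.

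**The case against.** The strongest reply is that nothing in the plan is broken. The trial was sized on an unadjusted SD, its 90% power is met without baseline OSS, and adjusting for the minimisation factors matches the allocation method. That stands. A reader might infer from the missing covariate that the trial is underpowered or its estimate biased, and the documents support neither. Chance imbalance in baseline OSS is likewise not bias: with about 485 analysed per group it is expected to be small, and the confidence interval already allows for it.

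A second reply is that section 23.3 does not exclude further covariates, that section 23.9 contemplates prognostic factors, and that the SAP may complete the list. This also stands in part, so it would be too strong to say that the protocol rules baseline OSS out. But section 23.3 does state a covariate list for the primary model, and section 23.9 states a different and open one. That mismatch is in the protocol itself.

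A third reply is that the correlation may be low. One baseline score is recalled, and the other is taken within 21 days of a fracture, when strict immobilisation ends. Neither is a stable score for a long-standing condition. This is fair: at 0.1 the gain is negligible, and the protocol offers no figure that would settle it.

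Finally, a reader might infer that age enters the model only as the two minimisation bands, under and over 50. Section 23.3 does not state the form of the age term, so that criticism cannot be made from the text.

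**Conclusion.** The point holds as a recommendation to improve efficiency and to settle the covariate list. It is not an error in the design. Section 23.3 does not name a baseline score that is already mandatory before randomisation, and sections 23.3 and 23.9 do not agree on what is adjusted for.

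The possible gain runs from almost nothing (half-width 1.50, power 90.3% at r = 0.1) to material (1.31 and 96.3% at r = 0.5). It would count for more if self-directed care were slightly worse: at a true difference of −0.5, power is 73.7% without adjustment and 77.7% at r = 0.3. The direction is secure, since any non-zero partial correlation narrows the interval and one or two extra covariates cost essentially nothing with 970 analysed. The size rests wholly on the assumed correlation.

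**What to change.** Amend section 23.3 to prespecify post-injury baseline OSS as a continuous covariate in the primary model, alongside age and centre. Pre-injury OSS may be added as a second continuous covariate. The text should say whether it is included. State that each continuous secondary score (PROMIS, EQ-5D-5L, SEE) is adjusted for its own baseline and, for EQ-5D-5L, which of its two baselines is meant. Reword section 23.9 so that it refers to this same list in place of unnamed prognostic factors. Entering age as a continuous term is optional, but the form used should be stated.

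The cost is a few sentences in the protocol and the matching lines in the SAP. There is no new data collection, no added burden on participants and no change to the sample size. Because baseline questionnaires must be complete before randomisation, few baseline values should be missing. The change is best made before any comparative data are seen.

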# 9.3 Secondary objectives and outcome measures

Table 2: Secondary objectives and outcome measures

Objective	Outcome measure	Time point(s) of evaluation of this outcome measure	Data required	Source data (including location)
To compare shoulder pain and function between treatment groups at 2 and 4 months postrandomisation	OSS	Baseline* (retrospective pre- injury and post- injury), 2 and 4 months post- randomisation	OSS questionnaire	Participant questionnaire (entered directly into trial database or as paper questionnaire)
To compare upper extremity physical function between treatment groups	Patient-reported upper extremity function as measured by the Patient Reported Outcome Measurement Information System (PROMIS) Physical Function (Upper Extremity) score	Baseline*, 2, 4 and 6 months post-randomisation	PROMIS questionnaire	Participant questionnaire (entered directly into trial database or as paper questionnaire)
To compare health-related quality of life between treatment groups	Patient-reported health-related quality of life as measured by the EuroQol 5 Dimensions EQ- 5D-5L	Baseline* (retrospective pre- injury and post- injury) 2, 4 and 6 months post- randomisation	EQ-5D-5L questionnaire	Participant questionnaire (entered directly into trial database or as paper questionnaire)
To compare self-efficacy to exercise between treatment groups	Patient-reported confidence in ability to exercise as measured by the Self-Efficacy to Exercise (SEE) Scale	Baseline*, 2, 4 and 6 months post-randomisation	SEE Scale questionnaire	Participant questionnaire (entered directly into trial database or as paper questionnaire)
To compare the rates of complications between treatment groups	Bespoke participant questionnaire and site- completed Case Report Forms (CRFs)	Up to 6 months post randomisation	Participant questionnaire at 2, 4 and 6 months; Medical records	Participant questionnaire (entered directly into trial database or as paper questionnaire) and medical records

Objective	Outcome measure	Time point(s) of evaluation of this	Data required	Source data (including
		outcome measure		location)
To assess costs	Bespoke	2, 4 and 6 months	Resource use	Participant
and	participant	post-randomisation.	questionnaire;	questionnaire
comparative	resource use		treatment	(entered directly
cost-	questionnaire;		CRF; EQ-5D-5L	into trial database
effectiveness	Site treatment		questionnaire	or as paper
	log; EQ-5D-5L			questionnaire)

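### Comparing complications is an unconditional secondary objective, but section 23.3 makes the comparison depend on the event count and names no between-group estimate when the model is not fitted

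*Protocol*

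**What the plan says.** Table 2 in Protocol section 9.3 gives the secondary objective as "To compare the rates of complications between treatment groups", up to 6 months after randomisation. No minimum number of events is attached to it. Section 9.7.4 lists what is counted: one participant-reported item (prolonged pain after exercise needing medication or a medical consultation) and six items that sites report from medical records.

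Section 23.3 gives the analysis. The number and proportion with complications will be "summarised by treatment group and compared using an adjusted logistic regression model if sufficient complications occur". The protocol does not define the threshold, does not name the effect measure, and states no between-group quantity for the case where the model is not fitted.

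Section 23.8 says that "secondary outcome analyses will use a two-sided 5% significance and 95% confidence intervals throughout".

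The only margin in the protocol is the 2.5 points on the Oxford Shoulder Score in section 23.2. Complications have none. No complication rates are given either; section 13.1 says only that a small proportion of participants are expected to have fracture or recovery complications.

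**The concern.** The objective and the analysis rule do not match. Section 9.3 promises a comparison. Section 23.3 makes it depend on how many events are observed and leaves only per-group summaries below an undefined threshold. This is a rule that the protocol states, not a detail it leaves open: a statistical analysis plan could define the threshold, follow 23.3 faithfully, and still leave the objective without a between-group estimate.

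The rule also ties the comparison to the method that most needs events. An adjusted logistic model is unstable when events are sparse. A risk difference with a score-type interval is not, and on the absolute scale its interval is narrowest when events are rare.

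At stake is how the complications are reported beside the primary result. The trial asks whether patients given one advice session lose out compared with supervised physiotherapy. If the shoulder score is non-inferior and a listed complication is rare, the planned report would show two counts and leave readers to work out for themselves how large a difference those counts are compatible with.

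**Working it through.** **Inputs.** From section 23.2: "Primary outcome data provided by 970 participants at 6 months will provide 90% power at 2.5% (1-sided) significance"; "minimum clinically important difference (MCID) of 5 points and a standard deviation of 12"; "based on a non-inferiority margin of 2.5"; "Allowing 20% loss to follow-up yields an overall sample size of 1214 (607 per group"). From section 15.3: 1:1 allocation. Event counts are assumed, because the protocol gives no rates.

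**The plan's own figure.** This fixes the group sizes used below. With a true difference of zero:

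n per group = 2 × (1.960 + 1.2816)² × 12² / 2.5² = 484.2, rounded up to 485, so 970 in total.

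485 / 0.8 = 606.25, rounded up to 607, so 1214 in total.

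Both stated figures reproduce, and the point below does not affect them. The calculations use 607 per group (everyone randomised, the natural denominator for events taken from medical records) and 485 per group (after 20% loss, relevant to the participant-reported item).

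**Interval for the risk difference (Newcombe).** For x events in n, with p = x/n and z = 1.960, the Wilson limits are

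(l, u) = [p + z²/(2n) ± z √{p(1−p)/n + z²/(4n²)}] / (1 + z²/n).

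For self-directed (1) minus usual care (2), with d = p₁ − p₂:

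lower = d − √{(p₁ − l₁)² + (u₂ − p₂)²}

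upper = d + √{(u₁ − p₁)² + (p₂ − l₂)²}

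**Worked case, 3 v 3 events, 607 per group.** p = 3/607 = 0.494%. Wilson limits: 0.168% and 1.443%. Then d = 0 and the half-width is √{(1.443 − 0.494)² + (0.494 − 0.168)²} = √(0.901 + 0.106) = 1.00 percentage points.

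**Same case, 485 per group.** p = 3/485 = 0.619%. Wilson limits: 0.211% and 1.803%. The half-width is √{(1.803 − 0.619)² + (0.619 − 0.211)²} = √(1.402 + 0.166) = 1.25 points.

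**Other assumed counts** (95% interval, percentage points):

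| Events, self-directed v usual care | 607 per group | 485 per group |
|---|---|---|
| 0 v 0 | −0.63 to +0.63 | −0.79 to +0.79 |
| 3 v 3 | −1.00 to +1.00 | −1.25 to +1.25 |
| 6 v 3 | −0.59 to +1.69 | −0.74 to +2.11 |
| 6 v 6 | −1.27 to +1.27 | −1.58 to +1.58 |
| 12 v 12 | −1.67 to +1.67 | −2.09 to +2.09 |
| 61 v 61 | −3.41 to +3.41 | −4.20 to +4.20 |

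**Relative scale, for contrast.** For 3 v 3 of 607, the crude odds ratio is 1 with standard error of its logarithm √(2/3 + 2/604) = 0.819. The 95% interval is exp(±1.96 × 0.819) = 0.20 to 4.97, which says little. The same six events limit the absolute difference to about one percentage point either way.

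The table shows that the interval exists at every count, including zero events in both groups, and is tightest in the sparse cases where section 23.3 names no comparison.

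**The case against.** The strongest reply is that this belongs in the statistical analysis plan. Section 23.1 says the protocol only summarises the statistics, and the event threshold, effect measure and sparse-event method are usual content for that document. This stands for the definition of the threshold. It does not answer the mismatch, because the conditional rule itself is in the protocol and contradicts an unconditional objective in the same document.

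A second reply is that section 23.8 already requires 95% intervals for secondary outcomes. It can be read that way. But 23.3 names no estimate to which an interval could attach when the model is not fitted, so the two sections need reconciling.

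Several stronger readings are tempting, and the protocol does not support them:

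- *The trial would report no bound on excess harm.* A fitted model carries a 95% interval under 23.8, and the analysis plan, not shown here, may add one for the sparse case.
- *The comparison would be an odds ratio judged only by a p-value.* The protocol names logistic regression but no effect measure, and an adjusted risk difference can be derived from the same model.
- *The information is discarded.* Counts and proportions by group are always reported, so a reader can compute a crude interval.
- *The test has too little power for rare complications.* The trial is powered only for the shoulder score. Low power for rare secondary events is not an error in the plan, and the change proposed here would not alter it.
- *Safety conclusions should be required to rest on an upper limit.* No margin is set for complications, so there is nothing to judge such a limit against.

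Finally, rarity is an assumption. The participant-reported pain item has no stated rate and may be common enough for the model to be fitted without difficulty.

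**Conclusion.** The point holds as a mismatch within the protocol. An unconditional secondary objective (9.3) is served by a comparison that depends on the observed event count (23.3), with no between-group estimate or interval named when the model is not fitted, and with an unclear relation to the intervals promised in 23.8.

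Its practical size is modest. It bites only if events are too few to model, which is more plausible for individual site-reported complications than for the pain item or for any complication combined. In that case a planned interval would still be informative: with equal counts of up to 6 per group, no wider than about ±1.3 percentage points at 607 per group or ±1.6 at 485. These figures rest on assumed event counts and on unadjusted Newcombe intervals. The primary analysis and the sample size are unaffected.

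**What to change.** In section 23.3, replace the conditional comparison with wording such as: *For any complication and for each listed complication, the risk difference (self-directed minus usual care) will be reported with a 95% confidence interval (Newcombe or Miettinen-Nurminen), whatever the number of events. An adjusted logistic regression, with its 95% confidence interval, will be added where event numbers allow.* The analysis plan can then define when numbers allow the adjusted model.

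This brings 23.3 into line with the objective in 9.3 and the intervals in 23.8. It costs one sentence and one extra column in the complications table, with no new data, no extra participants and no change to the sample size. The small downside is that the sparse-event intervals are not adjusted for age and centre.
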